10.1.3 Events of Special Interest

The following events of special interest (EOSI) need to be reported to the Sponsor within 24 hours of site awareness, irrespective of seriousness, severity or causality:

- Fracture
- Slipped capital femoral epiphysis
- Avascular necrosis or osteonecrosis

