10.2.3.2 Severity

Severity (as in mild, moderate, or severe headache) is not equivalent to seriousness, which is based on subject/event outcome or action criteria usually associated with events that pose a threat to a subject’s life or functioning. The severity of each will be assessed using the defined categories in Table 10.2.3.2.1.

The investigator will determine the severity of each AE and SAE [and EOSI, if applicable] using the National Cancer Institute (NCI) CTCAE v4. Adverse events that do not have a corresponding CTCAE term will be assessed according to the general guidelines for grading used in the CTCAE v4 as stated below.

Table 10.2.3.2.1: Adverse Event Grading (Severity) Scale

Grade	Description	
1	Mild: asymptomatic or mild symptoms; clinical or diagnostic observations only; intervention not indicated	
2	Moderate: minimal, local or noninvasive intervention indicated; limiting age-appropriate instrumental ADL ^a	
3	Severe or medically significant but not immediately life-threatening: hospitalization or prolongation of hospitalization indicated; disabling; limiting self-care ADL ^b	
4	Life threatening consequences; urgent intervention indicated	Grade 4 and 5 AEs should always be reported as SAEs
5	Death related to AE	

^a Instrumental ADL refers to the following examples: preparing meals, shopping for groceries or clothes, using the telephone, managing money.

^b Self-care ADL refer to the following examples: bathing, dressing and undressing, feeding oneself, using the toilet, taking medications, not bedridden.

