**Study 111-301 Statistical Analysis Plan****10 MEDICAL HISTORY**

Medical history will be solicited from each subject, including all major illnesses, diagnoses, and surgeries that the subject has ever had; any prior or existing medical conditions that might interfere with study participation or safety; and evaluation for knee, thigh, hip or groin pain, or change in gait/activity. All medical history terms will be coded in accordance with MedDRA Version 22 so that each term is assigned a system organ class (SOC) and preferred term (PT).

A predefined list of the achondroplasia-related PTs is provided in a separate project-level document. Prior to the database lock and unblinding of this study, any PTs which have not previously been reported as achondroplasia-related will be identified via medical review, and will be added to this list. The complete list of final terms will be retained in the study file, and documented in the CSR.

All recorded medical history will be summarized on the FAS by system organ class (SOC) and by preferred term (PT), ordered by descending order of frequency of SOC in the overall population. In addition, achondroplasia-related medical history will be summarized separately by SOC and PT in a similar manner.

The number of subjects with abnormal physical exam results at screening will be summarized and listed.

PI

A large rectangular area of the document is redacted with a solid light blue color, covering the text that would follow the "PI" label.

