15.1.2 Events of Interest

Events of interest (EOI) will be summarized by PT and treatment group.

The following are identified as events of interest:

Injection site reactions (ISR)

Study 111-301 Statistical Analysis Plan

- TEAEs with a MedDRA High Level Term (HLT) of “Injection site reaction”.

Hypotension

- TEAEs with PT: Blood pressure ambulatory decreased, Blood pressure decreased, Blood pressure diastolic decreased, Blood pressure orthostatic decreased, Blood pressure systolic decreased, Blood pressure systolic inspiratory decreased, Diastolic hypotension, Hypotension, Orthostatic hypotension.

Heart rate change

- TEAEs with a PT: Atrial tachycardia, Postural orthostatic tachycardia syndrome, Rebound tachycardia, Sinus tachycardia, Supraventricular tachycardia, Tachycardia, Tachycardia paroxysmal, Ventricular tachycardia, Bradycardia.

Hypersensitivity SMQ

- TEAEs with a PT included in the MedDRA hypersensitivity SMQ

Algorithmic Anaphylaxis SMQ (with sponsor-defined time restrictions)

- TEAEs with a PT included in the MedDRA anaphylactic reaction SMQ, with an additional time restriction: a narrow scope PT at any time, or two broad scope PTs from different classes where both PTs are within 24 hours of the same dose.

Fractures

- TEAEs with a MedDRA HLT: Fractures NEC, Limb fractures, Pelvic fractures, Skull and face fractures, Spinal column fractures, thoracic cage fractures non-spinal

Slipped Capital Femoral Epiphysis (SCFE)

- TEAEs with a PT: Epiphyseal disorder, Epiphyseal injury

Avascular necrosis and osteonecrosis

- TEAEs with a PT: Osteonecrosis, Osteonecrosis of jaw, Osteonecrosis of external auditory canal, Necrosis ischaemic

[figure not shown]
Events of interest will be summarized as follows:

- Incidence and exposure-adjusted event rates of injection site reaction events by PT
- Incidence and exposure-adjusted event rates of injection site reaction events by PT and duration of ISR (≤ 15 min, > 15 min and ≤ 60 min, > 60 min and ≤ 120 min, > 120 min and ≤ 24 hours, > 24 hours)
- Incidence and exposure-adjusted event rates of hypotension by PT
- Incidence and exposure-adjusted event rates of heart rate change events by PT
- Incidence and exposure-adjusted event rates of hypersensitivity (SMQ)

	Study 111-301 Statistical Analysis Plan
---	--

- Profile of injection site reaction events
- Profile of hypotension
- Profile of heart rate change events

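### The SAP's SCFE category rests on two generic epiphyseal terms, with no hip or slippage condition and no stated link to the sites' named SCFE reports

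*SAP*

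**What the plan says.** Protocol 10.1.3 lists three events of special interest: fracture, "Slipped capital femoral epiphysis", and avascular necrosis or osteonecrosis. These "need to be reported to the Sponsor within 24 hours of site awareness, irrespective of seriousness, severity or causality". SCFE is therefore collected under its clinical name.

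SAP 15.1.2 has a category headed with the same diagnosis. Its whole content is "TEAEs with a PT: Epiphyseal disorder, Epiphyseal injury". The general reporting rule in that section is "Events of interest (EOI) will be summarized by PT and treatment group". The outputs then itemized cover injection site reactions, hypotension, heart rate change and hypersensitivity; none is named for SCFE.

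Elsewhere the SAP adds to plain term searches. For achondroplasia-related medical history, SAP 10 provides that before lock and unblinding "any PTs which have not previously been reported as achondroplasia-related will be identified via medical review". SAP 15.1.1 extends this to adverse events, all of which are to be looked through before database lock so that the achondroplasia-related list can be updated. SAP 15.1.2 adds a time restriction to the anaphylaxis query. SAP 15.1.3 draws injection site symptoms from a dedicated eCRF page as well as from the adverse event page.

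**The concern.** A category that carries a diagnosis in its title should hold the cases with that diagnosis. Here neither preferred term names the femoral head or a slip, and nothing in the rule supplies the missing condition. The category could hold events that are not SCFE, and its wording does not guarantee that it holds every event that is.

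The diagnosis matters in this trial. Protocol 9.2 expects the drug to act at open growth plates, and Protocol 7.1 reports adverse skeletal changes from exaggerated growth in animals with open growth plates. Protocol 9.3.2 excludes children with past SCFE, and the Schedule of Events sets hip clinical assessments at Screening, Week 26, Week 52 and early termination. Pelvic X-ray is scheduled only at Screening, and later hip imaging depends on clinical findings (Protocol 9.12.6.4 and 9.12.6.12). The investigator's diagnosis is thus the main evidence that a slip occurred, and the SCFE rule does not refer to it.

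**Working it through.** No arithmetic applies. The documents give no SCFE rate, no expected count, and no sensitivity or specificity for the term search. The check is a comparison of texts.

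**Step 1: path of a reported SCFE.** The site notifies the sponsor (Protocol 10.1.3). The event is also an adverse event, entered on the eCRF by diagnosis where one is known (Protocol 10.2.2 and 10.3.1.1). The sponsor assigns the preferred term from the entered wording (Protocol 10.3.1), using MedDRA 22 (SAP 15.1). SAP 15.1.2 then selects on the preferred term alone.

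**Step 2: the rule applied to each kind of event.**

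| Event | Preferred term assigned | Under the SCFE heading? | Correct? |
|---|---|---|---|
| SCFE | one of the two | yes | yes, but not distinguishable from the next row |
| Epiphyseal event at wrist, knee or elsewhere | one of the two | yes | no |
| SCFE | any other | no | no; still in the all-event tables |
| Other epiphyseal event | any other | no | yes |

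**Step 3: which rows the documents support.** The second row follows from the rule, because no site or slippage condition limits events carrying those terms. The third row depends on where MedDRA 22 places SCFE, which the documents do not state. A preferred term can group more specific lower-level terms, so a generic name is not evidence that SCFE falls outside it.

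**Step 4: whether other outputs resolve the ambiguity.** Display by preferred term separates the two terms from each other. It does not separate the first row of the table from the second: a line showing one epiphyseal injury could be a hip slip or a wrist injury. Hip assessments are listed by subject (SAP 15.8) and could help someone tracing an individual case, but they do not enter the category. Notifying the data monitoring committee of adverse events from clinically significant hip findings (Protocol 9.12.6.12) is oversight during the trial and does not define the reported count.

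**Step 5: link to the 24-hour reports.** The visible SAP text states none. SAP 22 records that the category was renamed from events of special interest to events of interest. The current section does not say how the two relate.

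**The case against.** The strongest defence is that nothing is lost. A slip under any preferred term appears in the tables of all treatment-emergent events, and in the serious-event table if serious (SAP 15.1.1). Protocol 14.4 lists all adverse events, and the safety analysis is descriptive. The special-interest provision is a notification duty and is not shown to create a separate dataset; the diagnosis reaches the coded data through the adverse event page. A preset term search is reproducible, and a broad one leans toward inclusion. Because the display is by term, a wrist injury would appear under its own term and not as an unlabelled SCFE count.

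Most of this stands, and it limits the point in three ways.

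- A reader might infer that confirmed slips will be missed. The documents do not support that: it depends on the MedDRA 22 mapping, and the loss would be from one category, not from the safety tables.
- A reader might infer that the sponsor disregards the site reports. The most that can be said is that no use of them is stated. Part of SAP 15.1.1 is redacted and a figure in 15.1.2 is not shown, so a further listing cannot be excluded.
- A reader might extend the criticism to the fracture and osteonecrosis definitions. No defect has been shown in either.

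The defence does not remove the central point. Display by term cannot say whether a femoral head slipped, even if every SCFE codes to these two terms. The pre-lock look at all adverse events in SAP 15.1.1 is for the achondroplasia-related list and is not directed at confirming SCFE.

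**Conclusion.** The point holds in limited form. The SCFE definition in SAP 15.1.2 is non-specific as written and has no stated tie to the diagnosis that Protocol 10.1.3 requires sites to report by name. Inclusion of epiphyseal events from other sites follows from the rule itself, on the assumption that such events take one of the two terms. Omission of a true SCFE is possible only if MedDRA 22 places it under another term, which the documents leave open; it would then remain in the all-event tables.

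No size can be given. One event among the 55 children planned per arm is 1/55 = 1.8%, but that holds for any single event in an arm of this size and does not measure expected misclassification.

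The primary and key secondary analyses are not affected. The change is worth making because the event is one of three that the protocol singles out, and the better definition uses information the trial already collects.

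**What to change.** In SAP 15.1.2, keep the two preferred terms as a search aid and define the SCFE event of interest as any treatment-emergent adverse event that meets either condition:

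- the investigator reported it as SCFE, in the verbatim adverse event term or in a report under Protocol 10.1.3; or
- a blinded review of verbatim terms before database lock confirms it as SCFE.

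Reconcile the resulting cases with the 24-hour reports, and show the anatomical site of every event found by the search, so that hip and non-hip events can be told apart. Record in the study file which preferred term SCFE takes in MedDRA 22; this settles the conditional part of the point.

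The cost is a few sentences in the SAP and a short blinded review, which could run alongside the pre-lock review of adverse events already planned in SAP 15.1.1. The downside is some medical judgement where the search is now purely programmatic; setting the criteria in writing beforehand would limit it. The change requires no additional visits or assessments, and the fracture and osteonecrosis definitions need no change on this account.

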15.1.3 Injection Site Reaction Symptoms

Injection site reactions (ISRs) associated with single symptoms are recorded on the AE page (as a single symptom). ISR's with multiple symptoms are recorded as an AE of "Injection Site Reaction" on the AE page and the associated individual symptoms are recorded on the ISR symptom page.

In order to describe all ISR symptoms recorded, summaries will be based on the data collected on the ISR Symptoms page and also those single symptoms recorded as an adverse event.

Incidence and exposure-adjusted event rates of ISR Symptoms will be summarized by PT and treatment group.

ISR Symptoms will be listed.

Study 111-301 Statistical Analysis Plan

15.2 Clinical Laboratory Tests

Clinical laboratory tests (hematology, chemistry and urinalysis), are performed at Screening, and pre-dose at Day 1, Day 10, Week 6, Week 13, Week 26, Week 39, Week 52 and the Safety Follow-up visit. This study uses a centralized laboratory. All laboratory results are presented using SI units. When results are reported beyond analytical ranges, the reported numeric value will be used and included in summaries.

All summary tables will include laboratory assessments from baseline up to 30 days post treatment discontinuation. PI [REDACTED]

?

Laboratory tests will be graded as low/normal/high based on laboratory normal ranges. In addition, for laboratory tests with CTC grading available, all non-missing numeric results will be used to determine CTC grade programmatically, based on CTCAE v4.0.

For the following parameters, the distinction is made between significantly low/high results:

- Glucose (Hypoglycemia/Hyperglycemia)
- Hemoglobin (Anemia/Hemoglobin increased)
- Lymphocytes (Lymphocyte count decreased/Lymphocyte count increased)
- Potassium (Hypokalemia/Hyperkalemia)
- Sodium (Hyponatremia/Hyponatremia)
- Calcium (Hypocalcemia/Hypercalcemia)

The absolute values for pre-dose laboratory results at each scheduled visit, change from baseline in pre-dose laboratory results, and percent change from baseline in pre-dose laboratory results at each scheduled visit will be summarized (n, mean, SD, median, 25th and 75th percentile, minimum, maximum) and presented by treatment group.

Shift tables from baseline to worst post-baseline value (including scheduled and unscheduled visits) based on the CTC grading (Normal – Grade 5) will be generated for each Lab parameter where CTCAE grading is available, excluding parameters where CTCAE Grade does not rely on quantitative results alone (e.g. potassium and uric acid). Percentages are based on the number of subjects with each Baseline CTCAE grade (Normal, Grade 1, Grade 2, Grade 3, Grade 4, Grade 5, Missing, Overall).

[figure not shown]
For laboratory tests where grades are not defined by CTCAE, or where CTCAE grading does not rely on quantitative results alone (e.g. potassium and uric acid), shift tables will be

	Study 111-301 Statistical Analysis Plan
---	--

generated using the low/normal/high classification to compare to baseline to the worst post-baseline value.

Line plots of the mean result (+/- SD) for the pre-dose absolute values by scheduled visit for each treatment group will be provided for the following parameters:

- Hematology: erythrocytes, hematocrit, hemoglobin, leukocytes, neutrophils, platelets.
- Chemistry: alanine aminotransferase, albumin, alkaline phosphatase, aspartate aminotransferase, bicarbonate, bilirubin, blood urea nitrogen, calcium, chloride, creatinine, direct bilirubin, glucose, lactate dehydrogenase, phosphate, potassium, protein, sodium, thyrotropin, vitamin D.

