- ^{bb.} All procedures/interventions/surgeries will be recorded after informed consent is obtained and after the first administration of study drug, until 4 weeks after either the last administration of study drug or the Early Termination visit. If a subject is discontinued from the study prematurely, all procedures/interventions/surgeries will be recorded at the Early Termination visit.
- ^{cc.} Contact by a study staff member to the caregiver will be required after the Week 6 visit every 4 weeks (± 10 days) when there are no study visits or contact in the preceding 4 weeks. During these contacts, study staff will ask about dose administration and seek information on AEs and SAEs by specific questioning. Information on all AEs and SAEs should be recorded in the subject's medical record and on the AE eCRF.
- ^{dd.} The 4-week safety follow up visit will be waived for subjects who enter BMN 111 study 111-302 within the 2-week period following last dose of study drug. If sponsor discontinues development program at any time, a 4-week safety follow-up visit should occur.

	Study 111-301 Amendment 4	Page 52
---	---------------------------	---------

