9.3.6 Duration of Subject Participation

The planned duration of subject participation in this study is approximately 60 weeks, including up to 4 weeks of screening. After screening, subjects randomized to BMN 111 or placebo will receive study treatment daily for 52 weeks. Following completion of 52 weeks, subjects will be followed for safety for an additional 4 weeks. After the Phase 3 study has been completed, subjects in both the BMN 111 treatment arm and the control arm of the study may be eligible to receive BMN 111 over the longer term. If the sponsor discontinues development program at any time, a 4-week safety follow-up visit should occur.

Subjects who are not eligible to receive BMN 111 in a separate study will return at Week 56 for the Safety Follow-Up visit to assess for any AEs that may have occurred following completion of dosing.

Follow-up assessments and procedures should be performed as outlined in the Study 111-301 Schedule of Events ([Table 9.1.1](#)).

Subjects who discontinue from study treatment will be asked to complete study assessments and procedures for the remainder of the study. If subjects discontinue from study treatment and decline to participate for the remainder of the study, they will be asked to return for a final follow-up visit 4 weeks after their last study visit, and the agreement should be documented.

Subjects will participate in the study until completion or until one of the following occurs: the subject withdraws consent and discontinues from the study, the subject is discontinued from the study at the discretion of the investigator or BioMarin (upon consultation and in agreement with the investigator) or the study is terminated.

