12.2.9 Week 52 (± 7 days)

- Physical examination.
- Tanner Stage of Pubertal Development.
- Menstrual history in female subjects (if applicable).
- Pregnancy test (urine or serum) for female subjects who have begun menses or are ≥ 10 years old.
- Vital signs (body temperature, heart rate, BP, respiratory rate).
- Anthropometric measurements.
- Weight.
- HRQoL questionnaires (PedsQL and QoLISSY).
- Functional Independence Assessment (WeeFIM).
- Child Behavior Checklist (CBCL).
- Hip clinical assessment.
- Sleep study (optional).
- ECG (post-dose).
- Clinical labs (hematology, chemistry, and urinalysis).
- Thyroid function tests.
- 25-hydroxy Vitamin D.
- Salivary cortisol.
- Serum prolactin.
- FSH/LH.
- Anti-BMN 111 immunogenicity assessments.
- Bone metabolism blood biomarkers.

BOMARIN [®]	Study 111-301 Amendment 4	Page 99
-----------------------------	---------------------------	---------

- Bone metabolism urine biomarkers.
- Genomic biomarkers (optional).
- BMN 111 activity urine biomarkers (cGMP).
- Urine chemistry.
- PK (full).
- DXA (BMD and BMC of whole body less head, spine).
- Hand and wrist X-ray (PA view, left side).
- Bilateral whole leg, AP only.
- Lumbar spine X-rays (AP and lateral views).
- Injection site photos (optional).
- Concomitant medications.
- BMN 111 or placebo administration.
- BMN 111 or placebo accountability.
- Adverse events.
- Procedures/interventions/surgeries.

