12.3 Week 56 (±7 Days) Safety Follow-Up Visit

- Physical examination.
- Menstrual history in female subjects (if applicable).
- Pregnancy test (urine or serum) for female subjects who have begun menses or are ≥ 10 years old.
- Vital signs (body temperature, heart rate, BP, respiratory rate).
- ECG.
- Clinical labs (hematology, chemistry, and urinalysis).
- Anti-BMN 111 immunogenicity assessments.
- Bone metabolism blood biomarkers.
- Bone metabolism urine biomarkers.
- Concomitant medications.
- Adverse events.
- Procedures/interventions/surgeries.

	Study 111-301 Amendment 4	Page 100
---	---------------------------	----------

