**Study 111-301 Statistical Analysis Plan****15 SAFETY EVALUATIONS**

The safety population will be used for all summaries where assessments/events are reported by treatment group.

Summary tables will include all safety events up to 30 days following treatment discontinuation. PI [REDACTED]

Safety will be assessed by examining the incidence, severity (determined using the Common Terminology Criteria for Adverse Events (CTCAE) version 4), and relationship to study drug of all treatment-emergent adverse events (TEAEs) reported during the study period. In addition, changes from baseline in clinical laboratory results and vital signs will be assessed.

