15.3 Vital Signs

Vital Signs (heart rate, systolic/diastolic blood pressure, respiratory rate and body temperature,) are assessed at Screening, Day 1, Day 2, Day 3, Day 10, Week 6, Week 13, Week 26, Week 39, Week 52 and the Safety Follow-up visit.

All summary tables will include vital signs recorded from baseline up to 30 days post treatment discontinuation.

The vital signs that are collected pre-dose and post-dose are:

- **Pre-dose:** body temperature, heart rate, systolic/diastolic blood pressure and respiratory rate.

Study 111-301 Statistical Analysis Plan

- **Post-dose:** heart rate and systolic/diastolic blood pressure only.
 - Day 1: 0-1 hr. (Q15min); 1-2hr (Q30min)
 - Day 2-3: 0-2 hr. (Q30min)
 - All other dosing visits: 0-1 hr. (Q30min)

The absolute values for pre-dose vital signs at each scheduled visit, and change from baseline in pre-dose vital signs at each scheduled visit will be summarized (n, mean, SD, median, 25th and 75th percentile, minimum, maximum) and presented by treatment group. Line plots will be generated which present the mean pre-dose absolute values (+/- SD) by scheduled visit for each treatment group.

In addition, for heart rate and systolic/diastolic blood pressure, pre-dose assessments, and change from pre-dose to multiple post-dose time points at each scheduled visit will be similarly summarized and presented by treatment group. Line plots will be generated which present the mean pre-dose and post-dose absolute values (+/- SD) by treatment group for each visit separately.

The percentage of subjects experiencing at least one instance of a decrease of 20% in diastolic blood pressure from pre-dose to post dose will be summarized [n(%)] by treatment group at Baseline, Day 2, Day 3, Day 10, Week 6, Week 13, Week 26, Week 39, and Week 52.

Shift tables (Diastolic BP <40mmHg, Diastolic BP \geq 40mmHg) from pre-dose to lowest post-dose value category (Diastolic BP <40mmHg, Diastolic BP \geq 40mmHg) will be generated by visit and at any time.

Shift tables (Diastolic BP <45mmHg, Diastolic BP \geq 45mmHg) from pre-dose to lowest post-dose value category (Diastolic BP <45mmHg, Diastolic BP \geq 45mmHg) will be generated by visit and at any time.

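### The SAP's 30-day cut-off for laboratory summary tables is shorter than the protocol's Safety Follow-Up window, so some on-time follow-up results could miss the worst-value shift tables

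*SAP*

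**What the plan says.** **Cut-off.** SAP 15.2: "All summary tables will include laboratory assessments from baseline up to 30 days post treatment discontinuation". SAP 15 has a general rule: "Summary tables will include all safety events up to 30 days following treatment discontinuation". SAP 15.3 repeats the limit for vital signs, and SAP 19 repeats it in the immunogenicity section, worded for safety events.

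**Timing of the last visit.** Protocol 12.3 sets the "Week 56 (±7 Days) Safety Follow-Up Visit", with laboratory tests, vital signs, ECG and antibody samples. Protocol 9.3.6: "Following completion of 52 weeks, subjects will be followed for safety for an additional 4 weeks". The Week 52 visit also has 7 days either side (Protocol 12.2.9).

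**Who attends.** A footnote to the Schedule of Events in Protocol 9.1 reads: "The 4-week safety follow up visit will be waived for subjects who enter BMN 111 study 111-302 within the 2-week period following last dose".

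**Early leavers.** Under Protocol 9.3.6, children who stop treatment and decline the rest of the study return 4 weeks after their last study visit. Under Protocol 10.2.1, AEs are collected for 4 weeks from the last dose or from the Early Termination visit, whichever ends later.

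**What enters the tables.** SAP 5 lists every assessment but summarizes only those that fall in an analysis window. It exempts the worst-post-baseline laboratory shift tables, for which it takes every assessment. Table 5.4.2 in SAP 5.4 ends at Week 52 (Day 344 to 386) and has no follow-up row.

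**The concern.** The cut-off falls inside the window of the visit that closes safety follow-up. Two children with the same laboratory abnormality, both seen on time, could be treated differently in the shift tables because one came on day 29 and the other on day 33.

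SAP 5 and SAP 15.2 also give a programmer two instructions for those tables: take every assessment, or stop at 30 days. Because Table 5.4.2 has no follow-up row, the shift tables are the main laboratory summary in which a follow-up value could appear at all.

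The children affected are not a random subset. Prompt entry into 111-302 waives the visit, and SAP 4.2 offers 111-302 to those who complete 52 weeks on randomized treatment. The group with follow-up data therefore includes those who stopped early, some of them for safety reasons.

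**Working it through.** The documents state no share of results affected, so there is no figure of theirs to reproduce.

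**Inputs**
- Cut-off: 30 days (SAP 15.2), counted here from last dose. The SAP does not say which date marks treatment discontinuation.
- Week 52 target: Day 365 (SAP Table 5.4.2), 7 days either side (Protocol 12.2.9). The Schedule of Events has a dose at this visit.
- Week 56 target: 56 × 7 + 1 = Day 393, so Day 386 to 400.

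**Step 1: follow-up window only.** With last dose on Day 365 the gap is 28 + f days, where f runs from −7 to +7. The range is 21 to 35 days. Days 31 to 35 are past the limit: 5/15 = 33%. If the last dose is on Day 364, the range is 22 to 36 and the share is 6/15 = 40%.

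**Step 2: both windows.** If Week 52 is w days off target and Week 56 stays tied to Day 393, the gap is 28 + f − w, from 14 to 42 days. It exceeds 30 when f − w ≥ 3. That holds for 12 + 11 + … + 1 = 78 of 15 × 15 = 225 combinations, or 34.7%.

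**Step 3: from days to results.** Steps 1 and 2 count calendar days. A share of results needs the distribution of actual visit days, which neither document gives. Under assumed shapes:

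| Assumed timing | Past day 30, Week 52 on target | Past day 30, Week 52 varying the same way |
|---|---|---|
| Even over the window | 33.3% | 34.7% |
| Triangular, peak on target | 23.4% (15/64) | 29.9% |
| Truncated normal, SD 4 days | 25.0% | 30.9% |
| Truncated normal, SD 3 days | 19.8% | 27.2% |
| Truncated normal, SD 2 days | 10.3% | 18.7% |
| Truncated normal, SD 1 day | 0.5% | 3.5% |

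If visits were never early and spread evenly over 0 to +7 days, the share would be 5/8 = 62.5%.

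**Step 4: number of children.** Attendance is not given. If 5%, 10% or 20% of 110 attended (5.5, 11 or 22 children), even timing would put 1.8, 3.7 or 7.3 visits past day 30.

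**Step 5: early leavers.** If dosing stopped d days before the last study visit or the Early Termination visit, the 4 weeks from that visit end 28 + d days after last dose. For d ≥ 3, a follow-up exactly on target, or an AE inside the protocol's own reporting period, can be past day 30.

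**Step 6: which tables.**
- *By-visit laboratory and vital-sign tables:* no follow-up window exists, so essentially all follow-up results are out whatever the cut-off.
- *Laboratory shift tables:* exposed, and SAP 5 and 15.2 conflict.
- *Overall (ever-positive) antibody incidence, SAP 19:* possibly exposed. Samples are drawn at follow-up, but the 30-day sentence there speaks of safety events. Titer summaries stop at Week 52.
- *AE tables:* completers' collection ends at 28 days, inside the limit. Early leavers are exposed through Step 5.
- *Vital-sign shift tables:* they compare pre-dose with post-dose, and no dose is given at Week 56. Not exposed.
- *ECG, SAP 15.4:* no 30-day limit of its own, and by-visit summaries go no later than Week 52. Not materially affected.

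**The case against.** The best defence is that the protocol sets no cut-off for summary tables, so a 30-day limit contradicts nothing. It acts as a filter on time since treatment, and the exception in SAP 5 can be read as lifting only the visit-window rule. Protocol 7.2.2 gives a mean half-life of 24.4 to 27.0 minutes with no accumulation, so a laboratory value on day 33 says little about drug effect. Amendment 4 lengthened follow-up for AEs, and a completer's AE period fits within 30 days. Every assessment is listed, and text after the 30-day sentence is redacted in SAP 15, 15.2 and 19.

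Much of this stands, and it keeps the point small. It does not remove it. The half-life argument applies equally to day 25, which is included, so it does not justify a boundary inside the visit window. The two SAP sections can be read together, but the text available does not tell a programmer to do so.

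A reader might infer that about a third of on-time follow-up results will be dropped from the safety tables generally. The documents do not support that. A third is a share of allowed days. By-visit tables omit the follow-up visit for a different reason. Completers' AEs fall inside the limit. Nothing leaves the listings.

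**Conclusion.** The mismatch is real and minor. An on-time follow-up laboratory result can fall 31 to 35 days after a Day 365 last dose, or up to 42 days when Week 52 is early and Week 56 late. It could then be missing from the worst-value shift tables and possibly from the overall antibody incidence. For early leavers, AEs collected as the protocol requires could miss the AE tables.

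The firm figure is 5 of 15 window days (33%). The share of results is unknown: about 0.5% to 35% under clustered or even timing, and more if visits run late. The number of children is also unknown, because the waiver for entry into 111-302 removes an unstated proportion. All of this takes last dose as the date of treatment discontinuation, and redacted text may qualify the rule. The primary and key secondary analyses are untouched.

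**What to change.** - In SAP 15, 15.2 and 19, replace 30 days with a limit counted from last dose that covers the protocol window: at least 35 days, or 42 days to cover both visit windows. SAP 15.3 can carry the same words for consistency.
- For children who leave the study when they stop treatment, include AEs through the end of the protocol's AE reporting period (Protocol 10.2.1).
- State in SAP 5 and SAP 15.2 that the worst-value shift tables use every assessment, scheduled or not, up to that limit.
- State in SAP 19 whether follow-up antibody samples count toward the overall incidence.

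Do not extend the tables through Week 56 or a fixed number of days, whichever is later. Children who stop treatment are encouraged to stay for assessments. One who stopped at Week 10 and attended Week 56 would add 56 − 10 = 46 weeks off drug to the treatment-arm tables.

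The cost is SAP wording and one programming parameter. The small downside is a slight departure from the 30-day convention and a few more off-drug days in the tables. By-visit tables would not change. Showing follow-up results there would need a new row in Table 5.4.2, which is a separate choice.
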